# 9 Data Collection, Handling and Record Keeping

## 9.1 Data Confidentiality

A service known as CommCare is being used to collect data. Whenever data is transmitted between one of the servers CommCare uses and the Android application, it is sent using HTTPS. Here are the standards incorporated;

- Encrypted server-client connections using HTTPS
- All access to the cloud infrastructure is protected behind a firewall and require unique VPN access permissions
- Data is transferred through channels monitored by intrusion monitoring systems
- Encrypted at-rest database and encrypted database backups every night
- Security management meets ISO 27001, PCI-DSS, SOC1, SOC2, SOC3, and HIPAA standards

The devices used to collect data are encrypted Android smartphones. The CommCare mobile application itself is password protected and data collected by the application is encrypted (AES 256-Bit Symmetric Encyption, fully HIPAA compliant). These are only connected to the internet when data is being uploaded via a WIFI connection. Currently the devices are only being used by the health promoters the days of the diabetes checks, which is usually just 2 or 3 days per month. As soon as all the checks have been completed the devices are returned to the health promoter main building where the data is sent using a WIFI connection and then erased from the device.

The data is stored with other hospital system data used in monitoring an infant nutrition program in a HIPAA compliant server (see above). This data essentially constitutes an aspect of the patient's medical record at the San Lucas Mission Hospital. Persons with access to this database will include SLM medical director [name], the coordinators of the CHW program, [name] (onsite data manager and software engineer), [name] (the PI), and [name] (co-investigator).

Any hard copies of study data will be stored in locked filing cabinets at CHW headquarters in Quixaya and/or San Lucas Mission Hospital. When not in use, smartphones will be stored in a locked cabinet at CHW headquarters in Quixaya.

Data used for analysis of study outcomes will be extracted from this secure online medical record and stored on a secure UW Health (DFMCH) server in a password-protected Access database and/or password-protected Excel files. Data may also be sent to UW Health email using the Stanford University secure email service, which is HIPAA compliant. This data will not be de-identified. This data will be shared securely with IRB personnel as needed for study monitoring.

### 9.1.1 Confidentiality of Subject Records

By signing the protocol, the Investigator agrees that an IRB representative may consult and/or copy study documents in order to verify CRF data. By signing the consent form, the subject agrees to this process. If study documents will be photocopied during the process of verifying CRF information, the subject will be identified by unique code only and full names and similar identifying information (such as medical record number or social security number) will be masked.

The Clinical Site Investigators will ensure that the identity of subjects will be protected. All study records will be maintained in a secure fashion with access limited to essential study personnel only. All study documents submitted to the Coordinating Center will have identifiers removed other than dates of birth and service and subjects will be identified with a study-specific identification number only. The Clinical Site Investigators will maintain, in a secure location, an enrollment log that includes subject identifying information and links subjects to their study-specific identification number.

Version #: 1.0

1

#### Deleted: ONA

Formatted: Add space between paragraphs of the same style, No bullets or numbering

Deleted: ONA

Deleted: web browser of the device

Deleted: 1

Deleted: TLS/

Deleted: <#>A+ certified server-client TLS

configuration

Deleted: using AES-256

Deleted: ISO 27001 security management certification via AWS data centers

Deleted: amazon web server

Deleted: a

[name]

## 9.2 Data Capture

### 9.2.1 Source Documents

The primary source documents used for this study will be the electronic forms generated by the diabetes smartphone application, which contain all clinical data entered by CHWs during enrollment and monthly visits. For patients who are referred to San Lucas Mission Hospital for emergency care or other reasons germane to the diabetes program, paper medical records generated by these encounters will also be evaluated.

### 9.2.2 Case Report Forms

Case report forms will be based on the electronic forms generated by the diabetes smartphone application.

### 9.2.2.1 Missing Data

The smartphone application will assist in ensuring complete data entry in that most fields are required before the CHW can proceed to the next section of the visit and most data is entered through the use of radio buttons, prepopulated list options, and parameter-limited text boxes. Retention and follow up of patients will be enhanced by visiting patients who miss monthly group visits at their homes. Only patients who completed follow up to each relevant time point (e.g. 6 months, 12 months) will be included in these analyses.

## 9.2.3 Data Collection Tools

We will not be using UW institutional data collection tools.

## 9.3 Data Management

Data constituting patients' medical records will be stored in a secure database as noted in section 9.1. Data used for research purposes will be derived from this clinical database and managed by [name]. This will be stored on a secure UW Health server in password-protected files.

### 9.4 Data Monitoring

The smartphone application used to carry out the protocols of the study and collect data has built-in consistency and range checks. [name] will upload patient data to the secure database after each round of patient visits and maintain the database. Site medical director [name] will review patient data for clinical supervision on a monthly basis, as will [name] for safety and outcome monitoring. [name] will meet with [name] at least every 2 weeks via Skype and as needed via email. [name] is in contact with [name] and the CHW coordinators on a daily basis. [name] will also meet with [name] and the CHW coordinators via Skype as needed.

### 9.5 Records Retention

Records will be kept for at least 7 years following the study

## 9.6 Specimen Banking

Not applicable

# 10 Assessment of Safety

## 10.1 Specifications of Safety Parameters

Version #: 1.0

[name]

- Documented hypoglycemia (blood glucose <70 mg/dL)

- Hypoglycemia requiring emergency transport to the hospital and/or hospitalization
- Instances in which the application provided an incorrect recommendation
- Patient death

### 10.1.1 Definition of Adverse Events (AE)

Adverse event means any untoward medical occurrence associated with the use of an intervention in humans, whether or not considered intervention-related (21 CFR 312.32 (a)).

For the purposes of this study, known and non-serious adverse effects of medications used in the study metformin, glibenclamide, and aspirin - which have been used for decades and have well-established safety profiles, will not be considered adverse events. Examples of such non-serious adverse effects include gastrointestinal side effects of metformin and hypoglycemia symptoms associated with glibenclamide (without documented hypoglycemia).

# 10.1.2 Definition of Serious Adverse Events (SAE)

An adverse program effect will include any serious adverse effect on health or safety or any lifethreatening problem or death caused by, or associated with, the diabetes treatment program, if that effect, problem, or death was not previously identified in nature, severity, or degree of incidence in the investigational plan or application, or any other unanticipated serious problem associated with the program that relates to the rights, safety, or welfare of subjects.

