### 2.7 Potential Risk and Benefits to Subjects

### 2.7.1 Known Potential Risks

Immediate risks

- The potential immediate risks include the risks of taking metformin, glibenclamide, or aspirin, medications which have been in use for decades and have well-established safety and side-effect profiles.
  - Metformin: The most common side effect of metformin is gastrointestinal distress (e.g. dyspepsia, nausea, vomiting, diarrhea). This usually improves with time and most patients can tolerate these side effects, with only 5% of patients discontinuing the drug completely because of them^36. The most serious reported adverse effect of metformin is lactic acidosis. However, the incidence of this has been found repeatedly to be exceedingly low. In fact, a 2010 Cochrane review found no cases of lactic acidosis over 70,490 patient-years of metformin use, even when patients with some renal impairment were included. Finally, metformin can cause vitamin B12 deficiency with long term use
  - Glibenclamide: The primary potential adverse effect of glibenclamide is hypoglycemia. The proportion of patients taking glibenclamide who will suffer an episode of severe hypoglycemia (requiring the assistance of another for treatment and/or hospitalization) is estimated to be 0.5%
     Aspirin: Significant potential adverse effects of aspirin include gastrointestinal toxicity,
  - hemorrhage, renal toxicity, and hypersensitivity reactions
- Risk of errors in medication administration or recommendations due to user error or application
  malfunction
- Discomfort with finger sticks for blood glucose and hemoglobin A1c measurements

Long-range risks

• Complications of medication adverse effects (e.g. anemia from metformin or aspirin use, renal insufficiency as a related to aspirin use)

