### 10.2.3 Expectedness

[name] will be responsible for determining whether an AE is expected or unexpected. An AE will be considered unexpected if the nature, severity, or frequency of the event is not consistent with the risk information previously described for the study medications (metformin, glibenclamide, and aspirin).

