# 10.4 Reporting procedures

# 10.4.1 Adverse Event Reporting

# 10.4.2 Serious adverse event reporting

All deaths and immediately life-threatening events, whether related or unrelated, will be recorded in an SAE report and submitted to the IRB within 24 hours of site awareness. For other SAEs, [name] shall complete an SAE report and submit to the IRB as soon as possible, but in no event later than 10 working days after the he first learns of the effect.

[name]

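### Section 10.1.2 builds unexpectedness into the SAE definition, so an anticipated hospitalization for hypoglycemia that is not immediately life-threatening is not an SAE as written

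*Combined protocol and SAP*

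**What the plan says.** Section 10.1.2 carries the SAE heading, but the term it defines is an adverse program effect: "An adverse program effect will include any serious adverse effect on health or safety", extended to life-threatening problems and deaths linked to the program. A condition follows: the event counts only if it "was not previously identified in nature, severity, or degree of incidence" in the plan or the application. The only other limb is "or any other unanticipated serious problem associated with the program". The section lists no seriousness criteria such as hospitalization, and no other SAE definition appears in the plan.

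Three other sections bear on this:

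- Section 10.2.3 treats expectedness as its own classification: "An AE will be considered unexpected if the nature, severity, or frequency of the event is not consistent" with the risk information given for the study drugs.
- Section 10.4.2 states: "All deaths and immediately life-threatening events, whether related or unrelated, will be recorded in an SAE report", due at the IRB within 24 hours. Other SAEs are due within 10 working days.
- Section 2.7.1 states: "The primary potential adverse effect of glibenclamide is hypoglycemia". It gives the share of glibenclamide patients with a severe episode ("requiring the assistance of another for treatment and/or hospitalization) is estimated to be 0.5" percent).

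**The concern.** Seriousness and expectedness are different attributes of an event. Seriousness determines whether a case gets an expedited individual report. Expectedness determines whether it changes what is known about risk. When the first is made conditional on the second, the serious harms that the plan itself foresees are the ones that fail the SAE definition.

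Here the most foreseeable serious harm is severe hypoglycemia on glibenclamide, titrated by community health workers with physician review after the visit. Section 11.2.1 provides no formal DSMB and 11.1.1 no independent audits, so prompt case reports to the IRB are the main outside check. At stake are the SAE classification, its reporting deadline and possibly its longer collection window.

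**Working it through.** The point is one of wording, so there is no stated figure to reproduce. The sections are compared first, and a calculation for scale follows.

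**1. Does hospitalized hypoglycemia count as previously identified?**

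- Nature: yes. Section 2.7.1 names hypoglycemia as glibenclamide's main adverse effect.
- Severity: yes. Section 2.7.1 describes episodes that need another person's help or hospitalization, and 10.5 describes those that need emergency transfer or hospitalization.
- Incidence: yes. It is 0.5% of patients in 2.6 and 2.7.1, and 7.4 to 57.7 episodes per 1000 person-years in 10.5.

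All three elements are on record, so an episode within these bounds fails the first limb of 10.1.2. It is not unanticipated, so it fails the second limb as well.

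**2. Does another route make it an SAE or a UP?**

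| Section | Condition | Result for a hypoglycemia hospitalization within the stated bounds, not immediately life-threatening |
|---|---|---|
| 10.1.3 | All three UP criteria, the first being unexpectedness | Not a UP |
| 10.4.2, first rule | Death or immediately life-threatening | Not covered |
| 10.4.2, other SAEs | Must already be an SAE, which leads back to 10.1.2 | Not covered |
| 10.1.1 | Removes only known effects that are non-serious | Remains an AE |
| 10.6 | AEs are also reported to the IRB | Reportable, no deadline given |
| 10.3 | 30 days after last participation for SAEs, 7 for non-serious AEs | 30 days not assured; arguably 7 |

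**3. Do the sections agree with each other?** No.

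- A death that is unrelated to the program, or of a kind already identified, is outside 10.1.2 but must go on an SAE report under 10.4.2.
- If every SAE is unexpected by definition, the expectedness rating in 10.2.3 can separate nothing among SAEs.

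**4. Scale.** Expected episodes = patients × years × rate, with 100 patients and 6 to 12 months as in 10.5. All patients are taken to be on glibenclamide throughout.

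- Low rate, 6 months: 100 × 0.5 × 0.0074 = 0.37
- Low rate, 12 months: 100 × 1 × 0.0074 = 0.74
- High rate, 6 months: 100 × 0.5 × 0.0577 = 2.885, about 2.9
- High rate, 12 months: 100 × 1 × 0.0577 = 5.77, about 5.8

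The Poisson chance of at least one episode is 1 − exp(−0.37) = 31% at the low end and 1 − exp(−5.77) = 99.7% at the high end.

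On the per-patient figure, 100 × 0.005 = 0.5 patients are expected, and the chance of at least one is 1 − 0.995^100 = 39%.

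**The case against.** The strongest reply is that these events are well watched. Hospitalized hypoglycemia is a primary safety endpoint (4.1.3, 10.1). Documented hypoglycemia is an event of special interest (10.4.4). More than 3 severe episodes prompt a protocol review and consideration of suspension (10.5). Data are reviewed monthly, with cumulative safety analyses at 3, 6, 9 and 12 months (10.6). Section 10.6 sends AEs to the IRB, and 11.2.1 does the same for safety issues. All of this stands. A reader might infer from 10.1.2 that the likeliest serious harms never reach the IRB, and the documents do not support that. What is missing is SAE status and a deadline. Section 10.4.1, on AE reporting, shows only a heading in the text available. Wording may have been lost in extraction, so nothing is inferred from the blank.

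Four further objections have some force:

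- **The opening verb of 10.1.2 could be read as non-exhaustive.** That is possible, but no other definition or list of criteria fills the gap.
- **An event beyond the identified severity or incidence still qualifies.** This is true, and it limits the point to events within the stated bounds. It also weakens any extension to aspirin-related GI bleeding. Section 2.7.1 names GI toxicity and hemorrhage but gives no incidence, so a reader who infers that such bleeds are plainly excluded goes further than the text.
- **The 7-day window is an inference.** Section 10.3 assigns it to non-serious AEs and does not say that a hospitalization outside 10.1.2 becomes non-serious. Hence arguably, not certainly.
- **The episode count is not the size of the gap.** This is correct. Glibenclamide is an add-on or alternative drug here (2.6, 6.5), and only episodes that are not immediately life-threatening are affected.

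**Conclusion.** The SAE definition is wrong as written. It makes seriousness depend on unexpectedness and cannot be squared with 10.2.3 or 10.4.2. A hypoglycemia hospitalization within the stated severity and incidence, and not immediately life-threatening, is neither an SAE nor a UP. It is still recorded, tracked, counted toward the halting review and reportable to the IRB as an AE. It loses the 10-working-day SAE report and arguably the 30-day rather than 7-day window.

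The 0.37 to 5.8 expected severe episodes rest on 100 patients, 6 to 12 months, the two rates in 10.5 and universal glibenclamide use. The last assumption makes the range an upper bound at those rates. The documents do not show what share would not be immediately life-threatening, so the number of misclassified events cannot be stated. The parallel monitoring means that the defect should be corrected but is not critical. It affects no efficacy result.

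**What to change.** Rewrite 10.1.2 so that an SAE is defined by seriousness criteria alone: death, life-threatening event, hospitalization or its prolongation, lasting disability, birth defect, or other medically important event. Remove the condition about prior identification and leave expectedness to 10.1.3 and 10.2.3.

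Two reconciliations are needed:

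- **With 10.4.2:** the deaths and immediately life-threatening events reported there should be a subset of what 10.1.2 defines.
- **With 10.3:** that section says diabetes complications such as angina and ulcers are not AEs. A definition based on seriousness would otherwise bring in a hospitalization for one of them, so the plan must say whether it counts.

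The cost is a revised paragraph, the two reconciliations and a few more SAE reports on the timeline already in 10.4.2. Any reports added by hospitalized complications cannot be counted, because the documents give no rate for them. No dose, visit, endpoint or sample size changes.

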# 10.1.3 Definition of Unanticipated Problems (UP)

OHRP considers unanticipated problems involving risks to participants or others to include, in general, any incident, experience, or outcome that meets all of the following criteria:

- Unexpected in terms of nature, severity, or frequency given (a) the research procedures that are
  described in the protocol-related documents, such as the IRB-approved research protocol and
  informed consent document; and (b) the characteristics of the participant population being studied;
- Related or possibly related to participation in the research ("possibly related" means there is a
  reasonable possibility that the incident, experience, or outcome may have been caused by the
  procedures involved in the research); and
- Suggests that the research places participants or others at a greater risk of harm (including physical, psychological, economic, or social harm) than was previously known or recognized.

This study will use the OHRP definition of UP.

## 10.2 Classification of an Adverse Event

#### 10.2.1 Severity of Event

The following guidelines will be used to describe severity.

Mild – Events require minimal or no treatment and do not interfere with the participant's daily activities. Moderate – Events result in a low level of inconvenience or concern with the therapeutic measures. Moderate events may cause some interference with functioning. Severe – Events interrupt a participant's usual daily activity and may require systemic drug therapy or other treatment. Severe events are usually potentially life-threatening or incapacitating.

### 10.2.2 Relationship to Study Agent

This study will use a binary assessment:

Version #: 1.0

[name]

- Related There is clear evidence to suggest a causal relationship, and other possible contributing factors can be ruled out
- Not Related Evidence exists that the event is definitely related to another etiology. There must be an alternative, definitive etiology documented by the clinician.

### 10.2.3 Expectedness

[name] will be responsible for determining whether an AE is expected or unexpected. An AE will be considered unexpected if the nature, severity, or frequency of the event is not consistent with the risk information previously described for the study medications (metformin, glibenclamide, and aspirin).

The occurrence of documented hypoglycemia (including hypoglycemia requiring emergency transport to SLMH), hypoglycemia symptoms requiring the assistance of another person for treatment, signs of GI bleeding in patients taking aspirin, and other adverse effects reported by patients that are not consistent with GI side effects of metformin or mild hypoglycemia associated with glibenclamide (miscellaneous adverse effects) will be recorded through the smartphone application used for program execution and data entry. Treatment of hypoglycemia, including emergency transport if needed, will also be executed and recorded according to the hypoglycemia protocol (Appendix 4). Patients who require transport to SLMH will be assessed and treated by [name] and his staff, who will record treatments administered and patient outcomes, including need for hospitalization and any serious sequelae of the hypoglycemic event, including death. Patients taking aspirin who are experiencing possible GI bleeding will have their aspirin discontinued and will be referred to [name], who will record the results of any diagnostic evaluation and treatment required. Miscellaneous adverse effects of medications recorded by CHWs will be reviewed by [name] during his review of monthly patient visits (see section on "Physician supervision" in the Study Procedures section) and he will direct CHWs to take corrective action based on his clinical judgement.

Following each monthly visit, [name] will review treatment for all patients in the program. If the recommendations provided by the application and carried out by the CHWs goes against his clinical judgement, he will contact the CHW coordinators and direct them on corrective action. They will then visit the patient to follow up on their clinical status and carry out the actions recommended by [name]. When these corrective actions are necessary, [name] will communicate this to [name] and [name], who will record the reason that [name] disagreed with application recommendations and the corrective action that was recommended and carried out. Once per month, [name] will also review all treatment data to assess for compliance to program protocols, correctness of application treatment recommendations, and occurrence of adverse events. He will communicate his findings to [name] (PI), [name], [name], and the CHW coordinators in order to allow for corrective action and

Version #: 1.0

[name]

ensure that the entire team is aware of all potential AEs. [name] will record all reportable events with start dates occurring any time after informed consent is obtained until 7 (for non-serious AEs) or 30 days (for SAEs) after the last day of study participation.

